1.10 Timetable/Schedule of Events

T=0: Subjects perform supervised eccentric curl exercises.

T=1: Subjects have the intervention and control oils applied topically to their proximal arms immediately after exercise is completed and are monitored for 15 minutes.

T=1+ 8hrs: Subjects have a second application of the intervention and control oils applied topically to their arms.

T=1+ 24hrs: Subjects have a third application of the intervention and control oils applied topically to their arms. They complete the visual analog survey for perceived DOMS.

T=1+ 48hrs: Subjects complete the visual analog survey for perceived DOMS again.

T=1+ 72hrs: Subjects complete the visual analog survey for perceived DOMS for the final time.

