Oils under the genus *Eucalyptus* and *Mentha* have been shown to have anti-inflammatory and analgesic properties. [5,6,7] Both have been shown to have inhibitory effects on nitrous oxide and reduce the activity of various inflammatory markers. [5,8] *Eucalyptus globulus* is predominantly comprised of 1,8-cineole, which can inhibit neutrophil migration and thereby reduce edema and inflammation. [9] Rodent studies have even shown that *Eucalyptus* may have antinociceptive effects similar to that of morphine [8], which is supported by the subjective pain relief it brought to patients following a total knee replacement. [10] *Mentha x piperita* has been studied for its topical analgesic effects in headache patients, and application appeared to help suppress temporal muscle activity. [11] Local application has been shown to have a cooling effect through alteration of the calcium channels for cool-receptors, which may be soothing. [12] With these benefits in mind, this study aims to identify and compare the effects of topical *Eucalyptus globulus* and *Mentha x piperita* oils in delayed onset muscle soreness in the older adult and elderly population.

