Participants will be divided equally into the *Mentha x piperita* or the *Eucalyptus globulus* group. A 2% oil mixture for topical application will be made with essential oils from SunRise Aromatics diluted in fractionated coconut oil per guidelines from the RJ Buckle Clinical Aromatherapy for Health Professionals course recommendations. Physiciansupervised eccentric exercise of the elbow flexors will be performed based on an adaptation of the method described by Weber. [14] Free weight dumbbells will provide resistance. The subject will be instructed to prolong the extension aspect of the curl to be five seconds long. They will repeat this motion for 10 or more repetitions until exhaustion, either due to the participant feeling they can no longer tolerate the five second eccentric aspect of the exercise or the investigator identifying that their form has faltered. If subjects reach exhaustion after the 10 repetitions minimum, they will rest for 1 minute. If they are unable to complete 10 repetitions at this weight, the resistance will be decreased to the next lowest weight and they will continue until exhaustion. This will continue until subjects reach exhaustion with the lowest resistance weight. Immediately following exercise, the participants will have the respective oil applied topically to their left upper extremity by the investigator. Their right upper extremity will serve as the control and no essential oil will be applied. Investigators will apply the oil without any use of massage technique and to only apply very superficial pressure. This application will be repeated 8 hours after exercise, when DOMS has been known to initiate, and at 24 hours after exercise, when DOMS may begin to peak.

Subject Safety

Vital signs will be measured prior to the initiation of exercise, including temperature, heart rate, blood pressure, and oxygen saturation. A physician will be notified of any abnormalities and the subject must be medically optimized prior to exercising. All exercise will be supervised by a physician. After the intervention is applied, subjects will be directly observed for 15 minutes by a physician to ensure no immediate adverse reactions occur. Vital signs will be repeated at the end of the observation period.

Nursing staff will be on-site in their usual capacity and physicians available on-call throughout the duration of the study. Medications are available at the facility if needed for any adverse events.

B. Data Points

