Subject outcomes will be based on a self-reported visual analog scale, which has previously been shown to have validity in subjectively quantifying perceived muscle soreness and used in prior studies. [14,16]. These outcomes will be recorded by investigators for both the intervention and control upper extremity at 24, 48, and 72 hours post-exercise.

C. Study Duration

Each subject will participate in this study for 72 hours. The overall study is anticipated to take place over a six month duration.

D. Endpoints

The primary endpoint will be a self-reported perceived muscle soreness using a visual analog scale. There are no secondary endpoints.

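### The timetable lists the third oil application before the 24 h soreness rating and gives no interval, so that rating can mix an immediate one-arm sensation with delayed soreness

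*Combined protocol and SAP*

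**What the plan says.** Section 1.3 A sets the application times: immediately after exercise, and then "This application will be repeated 8 hours after exercise, when DOMS has been known to initiate, and at 24 hours after exercise". Section 1.3 B has soreness "recorded by investigators for both the intervention and control upper extremity at 24, 48, and 72 hours post-exercise". Application and rating therefore coincide at 24 h only. Sections 1.3 and 1.9 do not say which comes first.

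Section 1.10 is the only place where the two events appear in a sequence. Its 24 h entry reads "third application of the intervention and control oils applied topically to their arms. They complete the visual analog survey for perceived DOMS". It states no interval and no rating before application.

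Three other statements bear on the point:

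- **Sensation.** Section 1.2, in the text that follows on from *Mentha x piperita*, says: "Local application has been shown to have a cooling effect through alteration of the calcium channels for cool-receptors, which may be soothing".
- **Control arm.** Section 1.3 A says: "Their right upper extremity will serve as the control and no essential oil will be applied". Section 1.6 A agrees that the control extremity is untreated. Section 1.10 differs: "Subjects have the intervention and control oils applied topically to their proximal arms immediately after exercise is completed".
- **Endpoint and analysis.** The visual analog scale (VAS) rating is the only endpoint, and no primary time point is named (1.3 D). The analysis is a one-way repeated measures ANOVA at 0.05 (6.1). Subjects rate themselves and know their oil from its smell (1.6 A).

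**The concern.** The trial targets soreness that develops over a day or more. If the 24 h rating is made on fresh oil, it can also pick up what the subject feels on the skin at that moment. The left-right comparison within a person does not cancel a sensation that is present on one arm only.

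Two comparisons are exposed. Oil versus control at 24 h could favour the oil without any change in delayed soreness. Oil versus oil, which is an objective in 1.1 A, could favour *Mentha*, because cooling is documented for that oil alone.

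The 24 h reading is one of three, and it falls at the start of the 24 to 48 h peak described in 1.2. If no rating is taken before application, the two components cannot be separated afterwards.

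**Working it through.** **1. Order of events at 24 h**

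| Section | Application at 24 h | VAS at 24 h | Order |
|---|---|---|---|
| 1.3 A | yes | not mentioned | none |
| 1.3 B | not mentioned | yes | none |
| 1.9 A | not mentioned | yes | none |
| 1.10 | listed first | listed second | by sentence order only |

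**2. Time from the latest application to each rating**

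- 24 h, rated after application: unstated, possibly very short.
- 24 h, rated before application: 24 − 8 = 16 h.
- 48 h: 48 − 24 = 24 h.
- 72 h: 72 − 24 = 48 h.

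Only the 24 h rating can fall on fresh oil.

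**3. Size, on assumed values**

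The documents give no effect of cooling on the VAS, no SD and no correlation. There is no figure in the plan to reproduce for this point. Inputs:

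- n = 10 per oil (1.5).
- Alpha 0.05 (6.1), taken as two-sided. Section 1.5 refers to one-tailed 0.05, so one-sided results are shown as well.
- Assumed: no effect on delayed soreness, and an immediate shift b at 24 h only, in SDs of the left-right difference, with b = 0.3, 0.5 or 0.7.
- Assumed: correlation ρ between the left-right differences at any two times of 0.3 to 0.7, with equal SD at each time.

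*24 h alone, one oil group.* Paired t test with 9 df and noncentrality b√10. The critical values are 2.262 (two-sided) and 1.833 (one-sided).

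| b | b√10 | Significant, two-sided | Significant, one-sided |
|---|---|---|---|
| 0.3 | 0.95 | 13.6% | 22% |
| 0.5 | 1.58 | 29.3% | 43% |
| 0.7 | 2.21 | 50.6% | 65% |

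*Mean of the three readings.* The shift becomes b/3 and the SD of the mean becomes √((1 + 2ρ)/3), so the standardized shift is (b/3)/√((1 + 2ρ)/3). For b = 0.5 and ρ = 0.3 it is 0.1667/0.7303 = 0.228. For b = 0.5 and ρ = 0.7 it is 0.1667/0.8944 = 0.186.

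| b | Significant, two-sided (ρ = 0.7 to 0.3) | Significant, one-sided (ρ = 0.7 to 0.3) |
|---|---|---|
| 0.3 | 6-7% | 9-11% |
| 0.5 | 8-10% | 14-16% |
| 0.7 | 11-15% | 19-24% |

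*Oil versus oil at 24 h, if only one oil cools.* Two-sample t test on the left-right differences, 18 df, noncentrality b√(10/2) = b√5, two-sided: 9.7%, 18.5% and 31.7% for the three values of b.

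With b = 0 every one of these rates would be 5%.

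**The case against.** The strongest case against has five parts.

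- **The order is inferred.** The 24 h entry is two sentences, with no word such as *then* or *after* and no interval. A reader might infer that the protocol prescribes rating within minutes of application. It does not say so. What stands is that the only sequence on paper has application first, and that nothing prevents a rating on fresh oil or an order that varies between subjects.
- **Cooling may be part of the effect.** Section 1.2 presents cooling among the benefits that motivate the trial, and the endpoint is perceived soreness. On that view, relief on fresh oil is a result rather than a bias. This is fair, and it rules out saying that the 24 h rating measures cooling instead of soreness. But the objective in 1.1 A is delayed onset soreness, and a blended rating cannot show which of the two changed.
- **The evidence covers one oil.** The documents report no cooling for *Eucalyptus*. This stands: for that group the shift is only a possibility.
- **A 24 h t test is not the planned analysis.** This also stands. The planned ANOVA is not specified closely enough to compute, and averaging the three readings reduces the excess considerably.
- **Reordering is not a full cure.** The three readings would still differ in the number of applications and the time since the last one. The scent would still reveal the treatment at every reading. Both points are correct.

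**Conclusion.** The concern holds as a risk to one of the three readings of the only endpoint. The timetable allows, and by its sentence order suggests, that the 24 h VAS is completed on freshly applied oil. The rating can then mix an immediate one-arm sensation with delayed soreness. The support is clearest for *Mentha x piperita*, and the oil-versus-oil comparison is exposed for that reason.

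The size is unknown. On the assumed shifts, the false-positive rate for a 24 h test is well above 5%, and for the three-reading average it is modestly above 5%. These figures show the sensitivity of the design; they do not estimate the actual bias.

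A reader might infer that all three readings are compromised, or that both oils are shown to cool. The documents support neither: the 48 h and 72 h ratings follow no fresh application, and cooling is described for one oil.

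The conclusion assumes that the control arm gets no essential oil, as 1.3 A and 1.6 A say. The control-oil wording in 1.10 conflicts with those sections and must be reconciled with them, because it determines which sensations differ between the arms.

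**What to change.** In 1.10 and 1.3 B, state that at the 24 h visit both arms are rated on the VAS before the third application, and that this rating is the one analysed. Reconcile the description of the control arm in 1.10 with 1.3 A and 1.6 A.

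The cost is about one sentence in each of the two sections. Application times, visits, staffing and sample size do not change. The change must be made before enrolment, since a missing rating before application cannot be recovered.

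The small loss is that immediate relief after application would not be measured. If the investigators want it, a second, separately labelled rating can be added after application and kept out of the primary analysis. The fix does not remove the expectation effect of a scent that cannot be masked; that limitation applies to all three readings and should be acknowledged in the report.

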2.2 Research Staff Training

All research staff will undergo a briefing of the protocol for this particular study and their respective roles. All investigators will be notified of any updates in protocol or procedures. All investigators have undergone CITI training.

2.3 Resources Available

At the facility there is a rehabilitation room available and weights that can be used to provide resistance for the exercise. There is also 24/7 nursing staff and physicians on-call that can assist in the event of any adverse consequences to participants. There is a medication room available that would have appropriate treatments for potential adverse outcomes such as rashes.

2.4 Research Sites

The research will occur at the Manor Health and Rehabilitation facility (under CentraState Medical Center, [name]), and the data will be analyzed at the Rutgers RWJMS at CentraState Family Medicine Residency Program office ([name]). CentraState Healthcare System and the Manor have provided an study site agreement indicating their support of this research. The Manor will not be engaged in research, and only Rutgers study staff members will engage in any research activities at this site.

3.0 Multi-Center Research

N/A

4.0 Subject Considerations

4.1 Subject Selection and Enrollment Considerations

A. Method to Identify Potential Subjects

Research staff will identify patients who are currently admitted at the facility for subacute rehabilitation or long-term care that meet the age criteria of 50 years or older

B. Recruitment Details

Potential subjects will be verbally informed of the opportunity to participate in the study by co-investigators [name] and [name] at the Manor Health and Rehabilitation center, and if interested full details allowing for informed consent would be provided by the investigators. Subjects will be informed that their decision to participate or not participate in the study would have no influence on their care at the facility.

C. Subject Screening

The co-investigators will administer a simple screening survey to interested subjects which identifies basic demographics, such as age, gender, and hand dominance, history of upper extremity injuries within the past 1 year, open proximal upper extremity wounds, any allergies/hypersensitivities to the oils involved. The patient's functional status for exercise based on the Duke Activity Status Index will also be assessed, and they must have a score equivalent to 3.5 or greater metabolic equivalents (METs). Potential subjects will sign a screening consent prior to partaking in this screening survey.

Inclusion Criteria

Subjects 50 years or older with no previous resistance training sessions in the past year and who are currently admitted at the Manor Health and Rehabilitation facility will be recruited.

Exclusion Criteria

Exclusion criteria included any history of musculoskeletal injury or weight bearing restrictions to the upper extremities within the past year. Participants cannot have any significant symptoms that would preclude them from exercising without medical clearance based on the American College of Sports Medicine's "Recommendations for Preparticipation Health Screening," [13] and those with an asymptomatic history of any cardiovascular, metabolic, or renal disease must have a functional capacity of at least >3.5 METs based on the Duke Activity Status Index to participate in the type of exercises that are part of this study, based on the American College of Sports Medicine's "2011 Compendium of Physical Activities." [20] Subjects with known adverse

Protocol Title: Topical Eucalyptus globulus and Mentha x piperita on muscle soreness in older adults and the elderly Protocol Version Date: V3.03.20.21

reaction or allergy to the essential oils or hypersensitivities to fragrances, any open upper extremity wounds or history of upper extremity skin grafts are excluded.

4.2 Secondary Subjects

None

4.3 Number of Subjects

A. Total Number of Subjects

We anticipate enrolling 20 subjects to participate, 10 in the *Mentha x piperita* group and 10 in the *Eucalyptus globulus* group.

B. Total Number of Subjects If Multicenter Study

N/A

C. Feasibility

It is feasible to enroll this number of subjects given there is a consistent population of residents within this facility that would meet the age criteria and, after discussion with physicians at this facility, would also meet the criteria for exercise clearance. The nature of the facility also allows for a continuous influx of patients to the subacute rehabilitation facility, which will allow for rolling enrollment into our study.

4.4 Consent Procedures

A. Consent Process

Location of Consent Process

The consent process will take place at the Manor Health and Rehabilitation facility.

Ongoing Consent

N/A

Individual Roles for Researchers Involved in Consent

Co-investigator [name] will obtain consent from participants. The principal investigator, [name], will be available to answer any questions or concerns from potential subjects if needed.

Consent Discussion Duration

Ten minutes of time will be allotted to discuss informed consent. Should the subject require any clarification or a longer timeframe, accommodations will be made.

Coercion or Undue Influence

Subjects will be informed this is an optional study and their medical care at the facility will not be influenced by their decision to participate or not. Subjects will be able to voice any concerns or questions they may have. Subjects will be able to leave the study at any point should they choose.

Subject Understanding

Subjects will be asked to repeat back what their role in the study would be. They will verbalize understanding prior to signing any consent forms.

B. Waiver or Alteration of Consent Process

N/A

C. Documentation of Consent

Documenting Consent

All subjects will sign a form of informed consent. They will keep a copy and another copy will be stored in a secure file which only the research staff has access to.

Waiver of Documentation Of Consent (i.e., will not obtain subject's signature)

N/A

4.5 Special Consent/Populations

A. Minors-Subjects Who Are Not Yet Adults

N/A

B. Wards of the State

N/A

C. Non-English-Speaking Subjects

N/A

D. Adults Unable to Consent / Decisionally Impaired Adults

We will only be recruiting adults that have the decision-making capacity to consent.

4.6 Economic Burden and/or Compensation for Subjects

A. Expenses

There will be no additional expense to the subjects participating in this research.

B. Compensation/Incentives

There will be no compensation or incentives for participating in this study.

C. Compensation Documentation

N/A

4.7 Risks of Harm/Potential for Benefits to Subjects

A. Description of Risks of Harm to Subjects

Reasonably Foreseeable Risks of Harm

Topical application of the essential oils carries a risk of a local dermatitis reaction. [17] In a German multicenter study with over 6000 subjects with pre-existing dermatitis, only 0.25% of subjects who received 2% topical *Eucalyptus* oil, and only 0.64% of subjects who received 2% *Mentha x piperita* oil experienced reactions. The maximum recommended dermal concentration for *Eucalyptus* is 20%, and for *Mentha x piperita* it is 5.4%, and so our study will utilize a concentration of 2%, well below those limits. [18,19]

Participating subjects will be performing exercises during the study which may put them at risk for musculoskeletal injury. Muscle soreness is an expected result of the study. Subjects will be monitored closely during exercise by a physician to ensure proper technique is used. If subjects experience any discomfort beyond the expected level of soreness medical attention will be available and alternative methods of pain or inflammation control will be provided.

Risk of Harm from an Intervention on a Subject with an Existing Condition

If a subject has a known hypersensitivity or allergy to peppermint, eucalyptus, or the carrier oil they are at increased risk for adverse reactions from the intervention, particularly local dermatitis and thus will be excluded from the study. Anyone with open proximal upper extremity wounds or a history of skin graft to the upper extremity will also be excluded. Those with known upper extremity injuries in the past year or upper extremity weight bearing restrictions that may predispose them to musculoskeletal injury from exercise will be excluded from participation as well.

Other Foreseeable Risks of Harm

As with any research there is the risk of breach of confidentiality. All subject data will be stored in a secure file on a restricted drive that only investigators have access to. Subjects will be assigned a random identifier number. Names of subjects and their corresponding identifier number will be stored in one file, and a separate file will list the identifier number and the study data. Subject privacy will be ensured as well, as the exercise for this study will occur in a private room and only study staff will be aware of subject's participation in the study.

Observation and Sensitive Information

N/A

- B. Procedures which Risk Harm to Embryo, Fetus, and/or Pregnant Subjects N/A
- C. Risks of Harm to Non-Subjects
- D. Assessment of Social Behavior Considerations N/A
 - E. Minimizing Risks of Harm

Subjects will have vital signs taken prior to initiating any form of exercise, and a physician will review them to ensure that the subject is medically optimized. All exercise will be closely observed by a physician to ensure proper form and minimize risk for injury, and nursing staff will be available for any assistance needed. If subjects feel in any way they are being harmed through these exercises they will be encouraged to cease participation in the study. Medical care will be available if any injuries do occur.

Physicians will be directly observing subjects for 15 minutes after the first oil application to ensure there are no immediate adverse effects, and vital signs will be repeated at the end of this observation period. Subjects will have nurses available throughout the entire duration of the study. Subjects with known hypersensitivities or allergies to these substances, or pre-existing asthma, will be excluded from participating.

Medications are available on-site that will be able to address any potential adverse effects. Topical creams or antihistamines will be available for any dermatitis, and should any severe systemic allergic reaction occur there are epinephrine injectable pens available as well. Nursing staff is present at the facility 24/7 to care for the subjects, and physicians are on-call as well. On-call physicians have the ability to promptly notify investigators of any concerns with study subjects.

To reduce risk of breach of confidentiality, all subject data will be stored in a secure file on a restricted drive that only investigators have access to. Subjects will be assigned a random identifier number. Names of subjects and their corresponding identifier number will be stored in one file, and a separate file will list the identifier number and the study data. Subject privacy will be ensured as well, as the exercise for this study will occur in a private room and only study staff will be aware of subject's participation in the study.

Certificate of Confidentiality

N/A

Provisions to Protect the Privacy Interests of Subjects

All aspects of this study involving the research subject will take place in an area with only the subject and the investigators present in order to protect their privacy. Any information that they feel uncomfortable disclosing will be omitted.

F. Potential Benefits to Subjects

Potential benefits to subjects include identifying a natural alternative for managing muscle soreness.

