1.9 Data Collection

A. Primary Data Collection

Location: Data collection will occur at the Manor Health and Rehabilitation Center ([name]). Permission has been granted by the director of this facility and by authorities with CentraState Healthcare System, which the Manor is owned by.

- Process of Data Collection: The investigators will oversee the collection of data in-person at the facility. Only Rutgers study staff will be involved in any research roles. Staff at the Manor Health and Rehabilitation will not be involved in the collection of data or treatment of subjects pertaining to this study, but will maintain their usual roles at the study site throughout the duration of this investigation.
- Timing and Frequency: Data collection will occur at the beginning of a subject's participation in order to collect demographic information, and then at 24, 48, and 72 hours following exercise to survey their perceived muscle soreness.
- Procedures for Audio/Visual Recording: There will be no recording of subjects.
- Study Instruments: Recruited subjects will complete a survey to collect demographic data, medical history, and allergies. Subjects will identify their perceived muscle soreness using a self-reported visual analog. They will complete this for both the control and intervention arm at 24, 48, and 72 hours post-exercise.
- Ethnographic Studies, Interviews, Or Observation: There will be no interviews or observational aspect to this study.
- Subject Identifiers: Each subject will be assigned to a random number associated with their name that will be stored in a password protected file on a secure drive. In a separate, also password protected, file the collected data will be stored with the associated subject's number
- B. Secondary Data Collection: No secondary data collection will occur.

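### Section 4.7 limits knowledge of participation to study staff, but its safety plan relies on facility clinicians to help with adverse events and to alert the investigators

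*Combined protocol and SAP*

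**What the plan says.** **Who knows.** Section 4.7 A (other foreseeable risks) and section 4.7 E (minimizing risks) each state that "only study staff will be aware of subject's participation in the study".

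**Who provides cover.** Section 4.7 E also says: "Nursing staff is present at the facility 24/7 to care for the subjects, and physicians are on-call as well". Section 1.3, under Subject Safety, says: "Nursing staff will be on-site in their usual capacity and physicians available on-call throughout the duration of the study". Section 2.3 lists the same people as a resource: "There is also 24/7 nursing staff and physicians on-call that can assist in the event of any adverse consequences to participants".

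**Who alerts the investigators.** Section 4.7 E: "On-call physicians have the ability to promptly notify investigators of any concerns with study subjects".

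**Who counts as study staff.** Section 1.9 reserves research roles for the university's study staff. Section 2.4 says the facility is not engaged in research. Section 2.2 provides a protocol briefing for research staff only.

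**Physician observation.** Section 1.3 gives 15 minutes of direct observation once the intervention has been applied and does not say which application. Section 1.10 lists 15 minutes of monitoring at T=1 and none at the later applications. Section 4.7 E ties the observation to the first application.

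**The concern.** The confidentiality promise and the notification route need opposite things. An on-call physician can raise a concern about a study subject only if the physician knows that the resident is one. If the promise is kept literally, that knowledge is withheld from the people who are on site or on call between study visits.

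Two things are at stake. The first is safety information. The subjects are aged 50 or over, in subacute rehabilitation or long-term care, and have exercised to exhaustion. The plan itself foresees dermatitis, systemic allergic reaction, musculoskeletal injury and soreness beyond the expected level. A clinician who sees one of these without the exposure history may not connect it with the study, and the investigators may hear of it late or not at all. The second is the accuracy of what subjects are told: the protocol states a limit on disclosure that its own safety plan has to cross in order to work.

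**Working it through.** The plan gives no figure to reproduce on this point. The check is one of consistency, with a little arithmetic for scale.

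**Step 1: are the facility clinicians study staff?** No. By sections 1.9, 2.2 and 2.4 they hold no research role, are not among those briefed, and work at a site not engaged in research. Section 2.3 lists the nurses and on-call physicians among the resources at the facility. Section 4.7 E has the on-call physicians notifying the investigators, which treats the two as separate groups.

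**Step 2: set the statements side by side.**

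| Statement | Where | What it requires |
|---|---|---|
| Only study staff know of participation | 4.7 A, 4.7 E | Facility nurses and on-call physicians do not know |
| Nurses and on-call physicians help with adverse events in participants | 1.3, 2.3, 4.7 E | Possible from signs and symptoms, but without the exposure history |
| On-call physicians notify investigators of concerns about study subjects | 4.7 E | They know who the subjects are |

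The first and third rows contradict each other. The second is weakened by the first but not ruled out.

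**Step 3: does another section resolve it?** The text available for this review describes no chart flag, handover, briefing of facility staff or investigator on-call rota.

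**Step 4: how much of follow-up lies between study contacts?** Sections 1.3 and 1.10 place contacts at about 0, 8, 24, 48 and 72 h. The gaps are 8 − 0 = 8, 24 − 8 = 16, 48 − 24 = 24 and 72 − 48 = 24 h. Their sum is 8 + 16 + 24 + 24 = 72 h. Apart from the short contacts themselves, this is the whole of each subject's participation.

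**Step 5: how likely is a skin reaction?** Section 4.7 A cites 0.25% for eucalyptus and 0.64% for peppermint, both at 2% and both in people with pre-existing dermatitis. I assume that these rates apply once per subject, that subjects are independent, and that there are 10 per group:

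- Expected number: 10 × 0.0025 + 10 × 0.0064 = 0.025 + 0.064 = 0.089.
- Chance of at least one: 1 − (0.9975^10 × 0.9936^10) = 0.085, about 8.5%.

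This leaves out injury and excess soreness, for which the documents give no rates.

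**Step 6: observation.** Section 4.7 E names the first application, section 1.10 shows monitoring at T=1 only, and section 1.3 sets no limit after describing all three applications. The three do not yield one rule.

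**The case against.** Several stronger readings are tempting, and the documents do not support them.

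- **That section 1.9 adds to the conflict.** It says "Staff at the Manor Health and Rehabilitation will not be involved in the collection of data or treatment of subjects pertaining to this study", but the same sentence keeps those staff in their usual roles. Ordinary care of a rash or an allergic reaction is a usual role, so 1.9 is compatible with the safety plan. It matters here only as evidence that facility staff are not study staff.
- **That the 8 h and 24 h applications have no stated observation.** Section 1.3 can be read as covering every application. The supportable point is that the sections differ.
- **That all rescue rests on facility staff.** Sections 4.7 A and 6.3 name no provider, and 6.3 has pain monitored throughout the 72 hours, which may mean by study staff.
- **That facility staff cannot act.** They can treat what they see. Subjects have decision-making capacity (4.5), repeat back their role and keep a copy of the consent form (4.4), so they can disclose participation. Section 1.6 says the fragrance cannot be masked. Study staff also return at each scheduled contact.
- **That the endpoint is biased.** Soreness could be treated as ordinary pain without the investigators knowing, but each subject is their own control. A systemic analgesic would reach both arms and would mainly dilute the contrast. The documents give no basis for claiming bias in favour of oil.

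A further caution is that the text between sections 1.10 and 2.2 and the consent form were not available for this review. Either might describe cover or disclosure.

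These objections narrow the point but do not remove it. A notification route should not depend on the subject volunteering the exposure, and the two statements in 4.7 E remain incompatible.

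**Conclusion.** The point stands as an internal inconsistency in section 4.7 that should be fixed, with moderate confidence. If the awareness sentence is followed literally, the notification route through on-call physicians in the same section loses its basis. What is missing is a planned way for treating clinicians to link an event to the oil or the exercise and report it. The ability to treat symptoms is not lost.

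The inconsistency applies to all 20 subjects and to nearly all of each 72 h period, but the length of the gaps measures exposure to the problem, not harm. Skin reactions are unlikely at the cited rates, and those rates may not carry over to this population: they come from people with pre-existing dermatitis, while this protocol excludes known allergy, hypersensitivity and asthma.

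The conclusion assumes that the unavailable text does not already provide for disclosure to the facility's clinicians. The differing statements on the 15-minute observation are a separate, smaller inconsistency, and no view is taken on which is right.

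**What to change.** 1. Reconcile the awareness sentence in sections 4.7 A and 4.7 E with the safety plan. One way is to reword both so that participation is known to study staff and to the facility clinicians caring for the subject, with the subject's consent to that disclosure.
2. Make an investigator contact available to those clinicians, so that the notification route in 4.7 E can work.
3. Check that the consent form says the same, and amend it if it does not.
4. Align sections 1.3, 1.10 and 4.7 E on which applications the 15-minute physician observation covers. The choice belongs to the investigators.

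The cost is a few sentences of protocol text, possibly one in the consent form, and a contact sheet. The downside is slightly wider disclosure of participation, limited to clinicians already treating the resident. No treatment, rescue or observation rule is proposed.
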